## **Inclusion criteria**

Researchers will limit the main analyses to only those participants who 1) meet criteria for struggling with loneliness, 2) are randomized to a condition in analyses (ie, those who consented to participate and completed the baseline measures), 3) did not indicate that they did not participate seriously at the end of the study, 4) completed the study only once, and 5) spent at least 3 minutes completing the study introduction and baseline measures (ie, were not clearly bots or speeding past most of the content).

Update February 20, 2023:

Due to many suspected bots and scammers taking the survey (particularly from 12/22/2022 to 1/22/2023), researchers identified an array of suspicious factors suggesting that the same person may have taken the survey multiple times or that some form of automated bot was used to complete the survey. Based on these criteria, researchers decided to add an

additional column to the dataset with a suspicion score for each response and another column indicating whether researchers consider the response as fraudulent, real, or likely fraudulent.

The factors that researchers identified as suspicious are as follow:

- Using windows NT 6
- Using android 9 or below
- Multiple IP Addresses with same first 8 digits, particularly when taken within a close time period
- Reporting that one found the study on facebook, Instagram, or Twitter after Dec 10, 2022 or Reddit after Jan 13, 2023
- Email address contains 6 numbers in a row and is from gmail
- Responses to the question about what they liked and what they would change about the intervention are specific and identical
- Reports one found the study on Researchmatch, but one is not on the Researchmatch email list
- Many participants completing each study session within a short amount of time, often using similar devices
- duration < 8 minutes if finished whole survey
- more than 5 responses with the exact same longitude and latitude, many have >20 or 30
- Researchers emailed suspected bots/scammers and asked them to indicate where they found the study and what they learned from participating in the study. In suspicious responses, one's email address did not match one's stated name, emails used broken English, and some email responses were highly similar to others. Many who took the survey within a few minutes of one another also replied to the emails within a few minutes of one another.

### *Missing data handling*

Although the researchers take efforts to avoid missing data (e.g., a financial incentive for completing the study and reminder emails), it is not necessary to impute missing data before performing a longitudinal mixed-model analysis (Twisk et al., 2013). Participants with missing data at some assessments will be included in the analysis and results will be modeled on the basis of the available data. For all analyses, researchers will use the standard  $p < 0.05$  criterion for determining statistical significance.

To test for faulty randomization, researchers will use chi-squared tests with Yates's continuity correction and t-tests with Welch's approximation of degrees of freedom and assuming unequal variance. If any effects are found, researchers will adjust for them using the confounding variable as a covariate in model testing and will note them in the interpretation of results. Researchers will also use these tests to check for differential dropout.

#### *Additional analyses*

1. Researchers will duplicate the main analysis with the subset of participants who did not meet criteria for struggling with loneliness and thereby participated in the study without being compensated.
2. Researchers will duplicate the main analysis with the subset of participants who completed the week 8 follow-up.
3. Researchers will duplicate the main analysis but will include the following covariates in the mixed-effects model: gender (multiple choice), age (continuous), ethnicity (categorical), sexual orientation (categorical), education level (categorical), socioeconomic status (continuous), if participants completed the study on a computer, tablet, or phone, and whether participants answered at least one written-response question.
4. Researchers will use a one-way ANOVA to test between-group differences in loneliness at 8-week follow-up. If the omnibus ANOVA produces a significant F-score, researchers will conduct two planned contrasts to compare the experimental condition to each other condition, and will compute Cohen's ds of these comparisons. Researchers will run the same ANOVA on the 4-week follow-up data. Researchers will also conduct these ANOVAs on secondary outcomes and at post-intervention for outcomes collected then.
5. Researchers will calculate Cohen's d effect sizes reflecting within-group intervention effects on the loneliness for each condition from baseline to 4-week and 8-week follow-ups. They will also do so for each secondary DV

6. Researchers will run four logistic regression models with dropout as the outcome baseline measures as predictors to determine if they predict which participants drop out either before completing the intervention, before the post-intervention questions, or before the 4- and 8-week follow-ups.

*Additional analyses testing exploratory hypotheses*

1. To compare change in mental health outcomes across presence of an insight experience, researchers will conduct a mixed-effects model with loneliness as the outcome, timepoint, insight experience, and the interaction between the two as predictors, and a participant identifier nested within experimental condition as a random intercept.
2. To test if baseline self-efficacy is associated with change in loneliness between baseline and week 8, researchers will run a mixed-effects model with loneliness as the outcome, timepoint, baseline self-efficacy (as measured by the GSE-6), and the interaction between the two as predictors, and a participant identifier nested within experimental condition as a random intercept.
3. To test if engagement with the intervention predicts change in loneliness, researchers will run a mixed-effects model with loneliness as the outcome, timepoint, engagement (measured as the number of characters entered across all text entry prompts within interventions), and the interaction between the two as predictors, and participant identifier nested within experimental condition as a random intercept.

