## **Hypotheses**

Researchers’ primary hypothesis is that participants randomized to the loneliness SSI will have greater reductions in self-reported loneliness between baseline and 8-week follow-up than those who are randomized to the active control SSI.

As secondary hypotheses, researchers predict greater improvements in distress (DASS-9), social anxiety, general self-efficacy, hopelessness, meaning and purpose in life, and adaptive actions and thoughts in the loneliness SSI condition relative to the control SSI. Researchers also hypothesize that participants who are randomized to the 3-week version of the loneliness intervention will report greater reductions in loneliness than those who are randomized to either the control condition or the 30-minute SSI.

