#### *Additional analyses*

1. Duplicate the main analysis with the subset of participants who did not meet criteria for struggling with distress and thereby participated in the study without being compensated.
2. Duplicate the main analysis comparing the change in distress from baseline to week 4 follow-up rather than to week 8.
3. Duplicate the main analysis with the subset of participants who completed the week 8 follow-up.
4. Duplicate the main analysis but with the following covariates included in the mixed-effects model: gender (multiple choice), age (continuous), ethnicity (categorical), sexual orientation (categorical), education level (categorical), socioeconomic status (continuous), and if participants completed the study on a computer, tablet, or phone.
5. Use a one-way ANOVA to test between-group differences in distress at 8-week follow-up. If the omnibus ANOVA produces a significant F-score, researchers will conduct two planned contrasts to compare the experimental condition to each other condition, and will

compute Cohen's ds of these comparisons. Researchers will run the same ANOVA on the 4-week follow-up data and at post-intervention for outcomes collected then. Researchers will also conduct these ANOVAs on secondary outcomes.

6. Calculate Cohen's d effect sizes reflecting within-group intervention effects on distress for each condition from baseline to 4-week and 8-week follow-ups.
7. Run four logistic regression models with dropout as the outcome baseline measures as predictors to determine if they predict which participants drop out either before completing the intervention, before the post-intervention questions, or before the 4- and 8-week follow-ups.
8. Duplicate the main analysis including data from suspected bots/scammers.

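### In the additional ANOVAs, between-group Cohen's ds appear only after a significant omnibus F, and Study 1's two contrasts cannot cover its three hypothesised loneliness comparisons

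*Combined protocol and SAP*

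**What the plan says.** Aim 1 (Study 1), Additional analyses, item 4, plans a supplementary test: "Researchers will use a one-way ANOVA to test between-group differences in loneliness at 8-week follow-up". It continues: "If the omnibus ANOVA produces a significant F-score, researchers will conduct two planned contrasts to compare the experimental condition to each other condition", and the same sentence ends by adding Cohen's "ds of these comparisons". The ANOVA is repeated at week 4, on secondary outcomes, and at post-intervention where data exist. Item 5 of Additional analyses in Studies 2 and 3 repeats the rule: "If the omnibus ANOVA produces a significant F-score, researchers will conduct two planned contrasts".

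Within-group effect sizes carry no such condition. Study 1, item 5, plans "effect sizes reflecting within-group intervention effects on the loneliness for each condition from baseline to 4-week and 8-week follow-ups"; item 6 in Studies 2 and 3 does the same.

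Study 1's Hypotheses section names three loneliness comparisons. The primary one is that "participants randomized to the loneliness SSI will have greater reductions in self-reported loneliness between baseline and 8-week follow-up" than those given the active control SSI. The 3-week arm is then predicted to show "greater reductions in loneliness than those who are randomized to either the control condition or the 30-minute SSI", which adds 3-week vs control and 3-week vs SSI.

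The main analysis in each study is a mixed model with time, condition and their interaction. It is not conditional on any omnibus test.

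**The concern.** An effect size that is calculated only when a test is significant is a selected effect size. The F statistic is large when the observed group differences are large, so the ds that survive overstate the truth on average. After a non-significant F, the plan would leave only uncontrolled pre-post ds in standardised form, which do not use the randomised comparison. Later readers, and anyone pooling these trials, would see either an inflated between-group d or none.

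The second matter is coverage. One condition set against each of the other two gives two contrasts. Study 1 hypothesises three and does not say which arm is the experimental condition, so one hypothesised comparison drops out of these analyses on either reading.

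**Working it through.** **Coverage, from the text alone**

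| Study 1 experimental condition is read as | Contrasts produced | Hypothesised comparison left out |
|---|---|---|
| SSI | SSI vs control; SSI vs 3-week | 3-week vs control |
| 3-week arm | 3-week vs control; 3-week vs SSI | SSI vs control (primary) |

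Studies 2 and 3 do not have this problem for their primary outcomes. Both hypothesised comparisons start from one arm (*Blu Surfer*, *Lonely Blu Surfer*), so two contrasts suffice.

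**How often the gate applies in Study 1.** Table 1 has six effectiveness outcomes with two follow-ups each, and two of them are also measured at post-intervention: 6 × 2 + 2 = 14 gated ANOVAs.

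**Size of the selection effect.** The plan gives no sample size, SD or effect size for these analyses, so there is no figure to reproduce. Assumptions: three equal arms of n, SD 1, true d of 0.30 for SSI vs control, two-sided 0.05 (the plan gives p < 0.05 without sidedness). For each simulated trial, with s² the pooled variance:

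- F = n × variance of the three arm means ÷ s², on 2 and 3(n − 1) df;
- contrast t = difference in means ÷ √(2s²/n);
- d = difference in means ÷ s.

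At 100 per arm:

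| True effect of third arm vs control | Contrast significant, no gate | Contrast significant, gated | Mean d given significant F |
|---|---|---|---|
| 0 | 56% | 48% | 0.38 |
| 0.15 | 56% | 43% | 0.42 |
| 0.30 | 56% | 48% | 0.38 |
| 0.45 | 56% | 55% | 0.33 |
| 0.60 | 56% | 56% | 0.31 |

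The inflation in the first three rows is 0.38/0.30 = 1.27 to 0.42/0.30 = 1.40, that is 27% to 40%. In the last two rows it is 2% to 9% (0.305/0.30 and 0.328/0.30). With the third arm at 0.15, F is significant in 45.5% of trials, so d would go unreported in 54.5%. With it at 0.30, the figures are 58.0% and 42.0%.

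Other assumed sizes, same true d of 0.30:

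- At 60 per arm, mean reported d is 0.45 to 0.50 with the third arm between 0 and 0.30.
- At 175 per arm (80% power without the gate), it is 0.33 to 0.35 over that range, and 0.30 with the third arm at 0.45 or 0.60.

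**Error rates if the gate is dropped.** Chance of at least one false claim when all three arms are equal:

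| Rule | Study 1, three contrasts | Studies 2 and 3, two contrasts |
|---|---|---|
| Gate on F | 5.0% | about 4.1% |
| No gate, no adjustment | 12.2% | about 9.0% |
| Primary at 0.05, Holm on the rest only | about 8.5% | about 9.0% |
| Primary first; others only if it succeeds | 5.0% | 5.0% |

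In the third rule, Studies 2 and 3 have only one non-primary contrast, so Holm adjusts nothing. The fourth rule holds at 5% in general. If the primary null is true, any false claim first needs a false primary rejection, which has a 5% chance. If it is false, only the remaining contrasts can err, and Holm across two (or a single test at 0.05) bounds that at 5%.

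**The case against.** The strongest reply is that an omnibus F before pairwise contrasts is a recognised procedure. With three arms it holds the familywise error of all pairwise comparisons at 5.0%. That stands, and it means the gate cannot simply be deleted if significance claims will be made. It justifies gating tests, however, not withholding estimates.

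A second reply is that the gated ANOVA is supplementary and concerns the score at follow-up, whereas the hypotheses concern change and are tested in the mixed model. That also stands. A reader might infer that the gate lowers the power of the primary test, but the documents do not support this: the time-by-condition model is fitted whatever F shows. Nor does a null F remove all between-group estimates, because the model still estimates differences in change and includes all three arms, so 3-week vs control can be estimated there. What the model section lacks is a named set of pairwise contrasts, a reference arm or a standardised effect, so it does not supply the missing ds.

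A third reply is that Study 1 predicts the 3-week arm to be best, and then the gate usually opens and the bias is small. That is right, and the last two table rows show it. Studies 2 and 3 predict the experimental arm to beat both others, so a third arm lying between the experimental arm and the primary comparator, the worst case, is plausible there.

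**Conclusion.** The point holds for the additional ANOVAs in all three studies. The rule makes the only planned between-group Cohen's ds depend on significance, and they will be biased upward. At an assumed 100 per arm and a true d of 0.30, the mean reported d is 0.38 to 0.42 if the third arm lies between the other two or equals one of them, and 0.31 to 0.33 if it is clearly better than the SSI. The bias grows with smaller arms and shrinks with larger ones. That the ds are selected follows from the text; its size rests on assumed sample sizes, equal arms and SD 1.

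In Study 1, two contrasts cannot cover three hypothesised comparisons, and which one is lost depends on an undefined term. It would go too far to say that 3-week vs control is never examined, or that it is certainly the omitted one. The primary mixed-model test is unaffected. This is a reporting defect worth correcting, not a threat to the primary result.

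**What to change.** In Additional analyses (Study 1, item 4; Studies 2 and 3, item 5), remove the condition on F from the estimates. State that the between-group difference, 95% CI and Cohen's d will be reported for every hypothesised contrast whatever the F result, and name the contrasts:

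- Study 1: SSI vs control (primary), 3-week vs control, 3-week vs SSI.
- Study 2: *Blu Surfer* vs *ABC Project* (primary), *Blu Surfer* vs online help-seeking as usual.
- Study 3: *Lonely Blu Surfer* vs *Sharing Feelings* (primary), *Lonely Blu Surfer* vs *Overcoming Loneliness*.

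Naming the arms also settles the undefined term in Study 1.

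If significance will be claimed from these contrasts without the gate, test the primary contrast first at 0.05 and the others only if it succeeds, with Holm across the two remaining contrasts in Study 1. Leaving the primary unadjusted and applying Holm only to the rest is not enough. This order controls error within one outcome at one time point, not across the 14 Study 1 ANOVAs.

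Cost: plan wording, no new data, and slightly more reporting. The real downside is that a non-primary contrast can be declared significant only after the primary one is.

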**Brief Internet Interventions to Support Mental Health Study Protocol**  
**(Includes analysis plans and information sheets)**

**April 6, 2023**

## **Aim 1: Evaluating a Single-session Intervention for Loneliness**

### **Procedure**

#### *Sample recruitment*

Researchers will use social media and the University of California, Irvine Social Ecology subject pool to recruit a diverse online sample of English-speaking participants aged 16+ with access to the internet and a computer, tablet, or smartphone. Researchers will advertise the study on social media using both paid and unpaid posts on several platforms, including Instagram, Reddit, Tumblr, Twitter, Facebook, LinkedIn, 4chan, and others. Researchers may also use the online subject recruitment platform Researchmatch.

Recruitment materials will explain that participants must be at least 16 years old, speak English, and have access to internet and a computer, smartphone, or tablet to be allowed to participate in the study. After a brief introduction to the study, researchers will first ask participants to complete the ULS-3 loneliness measure. To ensure a sufficient number of participants struggling with loneliness for analysis, if one's score on the measure meets the criterion for "struggling with loneliness", they will be invited to participate in the study and be offered a reimbursement of a \$10 Amazon gift card that researchers will email them once they complete the final follow-up 8 weeks later. Individuals will be considered to be struggling with loneliness if their score on the ULS-3 is 6 or higher and they answer affirmatively that their loneliness is causing them distress (Steptoe et al., 2013).

Researchers will only allow participants to complete the study once. If one's score on the loneliness measure does not meet the criterion, researchers will still give them the opportunity to complete the study without compensation. Researchers will also offer them access to the loneliness programs if they prefer to not participate in the study. Researchers will offer those who participate through the UC Irvine subject pool 1 hour of participation credit for completing the first part of the study. If UC Irvine subject pool participants meet criteria for struggling with distress, they will also be offered a \$10 gift card for completing all parts of the study.

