## **Analysis plan**

### *Main analysis*

The main DV is the change in loneliness (UCLA Loneliness Scale - 20 item Version 3) from baseline to 8-week follow-up. In the main analysis, researchers will test between-group differences across experimental conditions in change in loneliness from baseline to 8-week follow-up. Researchers will use a mixed-effects model predicting loneliness with condition, measurement time point, and the 2-way interaction between condition and time point as predictors and a participant identifier as a random intercept. Using the “lme4” package in R, these analyses will take the following form:

```
lmer(loneliness ~ time*condition + (1|study_id))
```

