#### *Additional analyses*

1. Duplicate the main analysis with the subset of participants who did not meet criteria for struggling with loneliness and thereby participated in the study without being compensated.

2. Duplicate the main analysis comparing the change in loneliness from baseline to week 4 follow-up rather than to week 8.
3. Duplicate the main analysis with the subset of participants who completed the week 8 follow-up.
4. Duplicate the main analysis but with the following covariates included in the mixed-effects model: gender (multiple choice), age (continuous), ethnicity (categorical), sexual orientation (categorical), education level (categorical), socioeconomic status (continuous), and if participants completed the study on a computer, tablet, or phone.
5. Use a one-way ANOVA to test between-group differences in loneliness at 8-week follow-up. If the omnibus ANOVA produces a significant F-score, researchers will conduct two planned contrasts to compare the experimental condition to each other condition, and will compute Cohen's ds of these comparisons. Researchers will run the same ANOVA on the 4-week follow-up data and at post-intervention for outcomes collected then. Researchers will also conduct these ANOVAs on secondary outcomes.
6. Calculate Cohen's d effect sizes reflecting within-group intervention effects on loneliness for each condition from baseline to 4-week and 8-week follow-ups.
7. Researchers will run four logistic regression models with dropout as the outcome baseline measures as predictors to determine if they predict which participants drop out either before completing the intervention, before the post-intervention questions, or before the 4- and 8-week follow-ups.
8. Duplicate the main analysis including data from suspected bots/scammers.

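### Within-arm pre-post Cohen's ds are labelled intervention effects and always reported, while between-arm ds are planned only after a significant omnibus F

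*Combined protocol and SAP*

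**What the plan says.** Aim 1, Additional analyses, item 5 plans "effect sizes reflecting within-group intervention effects on the loneliness for each condition", expressed as Cohen's d. These are to cover the change to week 4 and to week 8, and every secondary outcome as well. Item 6 of the same section in Study 2 ("effect sizes reflecting within-group intervention effects on distress for each condition") and in Study 3 ("effect sizes reflecting within-group intervention effects on loneliness for each condition") repeats the label, there for the primary outcome only. No condition attaches to any of these.

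The preceding item in each list (item 4 in Aim 1, item 5 in Studies 2 and 3) is a one-way ANOVA on follow-up scores. The two planned contrasts and their Cohen's ds follow only if the omnibus F is significant. The ANOVAs are also to be run at week 4 and on secondary outcomes.

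On the sample, Aim 1, Inclusion criteria, states: "Researchers will limit the main analyses to only those participants who 1) meet criteria for struggling with loneliness". The criterion, in Sample recruitment, is that "their score on the ULS-3 is 6 or higher and they answer affirmatively that their loneliness is causing them distress". Study 3 uses the same criterion. Study 2 uses a PHQ-4 depression or anxiety subscale score of at least 3. Both restrict their main analyses in the same way.

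The primary analysis in each study is a mixed model with a time-by-condition interaction. In Aim 1 it is to "test between-group differences across experimental conditions in change in loneliness from baseline to 8-week follow-up".

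**The concern.** The within-arm d answers the question of how much this arm changed. The label says it answers the question of what the intervention did. The two differ by everything else that moves scores over 4 or 8 weeks: natural course, the effect of answering the same questionnaire again, and regression to the mean. The last is a live possibility because entry to the main analysis set requires a high score on a screener related to the outcome.

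No arm shows what would happen without an assigned activity. Aim 1 and Study 3 use a supportive-therapy control session, and the third arm in Study 2 is a set period of guided browsing. The label also covers every condition, so the control arm's own change would be called an intervention effect.

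The conditional rule makes this worse. When the ANOVA is not significant, the plan drops the between-arm d and keeps the within-arm ds. That is when a reader most needs to see how small or how imprecise the randomised difference is. A null trial could then present beneficial ds in all three arms, with no standardised between-arm figure beside them.

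**Working it through.** The documents state no effect size, SD, retest correlation or screen-positive rate, so there is no figure of the plan's own to reproduce. The calculation below is an illustration. It asks how large a within-arm d regression to the mean alone could produce.

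**Model.** Screener S, baseline outcome B and week-8 outcome F are jointly normal with unit variance. There is no treatment effect and no true mean change. A fraction p screens positive (S > c).

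**Formulas.**
- Selection intensity: λ = φ(c)/p
- Mean fall among those selected: E[B − F | S > c] = (r_SB − r_SF) × λ
- Baseline SD among those selected: √(1 − r_SB² × k), with k = λ(λ − c)
- Within-arm d = mean fall ÷ that SD

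**Assumed inputs.** p = 30% to 70%; r_SB (screener with baseline outcome) = 0.7 to 0.8; r_SF (screener with week-8 outcome) = 0.5 to 0.7.

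**Middle case** (p = 0.5, r_SB = 0.8, r_SF = 0.6). Here c = 0, λ = 0.798 and k = 0.637. The mean fall is 0.2 × 0.798 = 0.160. The SD is √(1 − 0.64 × 0.637) = 0.770. So d = 0.160/0.770 = 0.21.

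**Largest case** (p = 0.3, 0.8/0.5). Here c = 0.524, λ = 1.159 and k = 0.736. The mean fall is 0.3 × 1.159 = 0.348. The SD is √(1 − 0.64 × 0.736) = 0.728. So d = 0.348/0.728 = 0.48.

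**Grid of within-arm d with no true effect:**

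| r_SB / r_SF | p = 0.3 | p = 0.5 | p = 0.7 |
|---|---|---|---|
| 0.8 / 0.5 | 0.48 | 0.31 | 0.18 |
| 0.8 / 0.6 | 0.32 | 0.21 | 0.12 |
| 0.8 / 0.7 | 0.16 | 0.10 | 0.06 |
| 0.7 / 0.5 | 0.29 | 0.19 | 0.11 |
| 0.7 / 0.6 | 0.14 | 0.10 | 0.06 |
| 0.7 / 0.7 | 0 | 0 | 0 |

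**Simulation check.** The middle case was simulated with 2,000,000 draws, correlation 0.7 between baseline and week 8, and random allocation to two arms. Standardised by the baseline SD, the within-arm d was 0.21 in both arms. The between-arm difference in change was 0.001 SD. Those below the cut-off moved the other way, with d = −0.21, as a selection artefact should.

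**What the model leaves out.** Natural course and repeat testing are not modelled and could add to or subtract from these figures. The scales are treated as continuous. The extra loneliness-distress question (Aim 1 and Study 3) and the either-subscale rule (Study 2) are reduced to a single cut-off.

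**The case against.** The strongest reply is that these ds are supplementary. Every efficacy hypothesis compares arms, and no test or decision rule uses a within-arm d. Because the ds are given for every condition, a reader can set the arms side by side. This stands, and it is why the point is minor. Setting arms side by side does not repair the label, however, and it gives neither an interval for the difference nor a single figure for it.

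A second reply is that regression to the mean is not assured. Selection is on the ULS-3 or PHQ-4, while the primary outcome is the ULS-20 or DASS-9. The artefact arises only if the screener correlates more strongly with the baseline outcome than with the week-8 outcome. This also stands. The screener and the baseline measures both come at intake, before the intervention, so shared transient state makes the condition plausible, but the documents do not establish it. A reader might infer that scores must fall, or must fall by some definite amount; neither follows.

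A reader might also infer that a null ANOVA leaves only within-arm estimates in the report. It does not. The mixed model runs regardless, and its interaction terms describe between-arm differences in change in scale points. What is lost is the between-arm Cohen's d for that outcome and time point.

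Finally, the within-arm items do not name their analysis set. The restriction is written for the main analyses, so applying it to these ds is the natural reading but an inference.

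**Conclusion.** The point holds as a minor matter of reporting and interpretation. Following the plan as written would describe uncontrolled change as intervention effect in all three studies, and would withhold the between-arm d when the omnibus F is not significant.

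The size cannot be fixed from the documents. Under the assumed ranges, regression to the mean alone gives a within-arm d from 0 to about 0.48. It is zero whenever the two screener correlations are equal. Even at zero the label would be wrong, because natural course and repeat testing remain in the change.

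The documents do not support the stronger conclusion, which a reader might draw, that the trials' efficacy findings are biased by this. Chance selection effects fall on all randomised arms alike, and the primary time-by-condition comparison is unaffected.

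**What to change.** Make two changes in the Additional analyses of all three studies.

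1. Rename the within-arm quantity (Aim 1 item 5; Studies 2 and 3 item 6) as *within-arm pre-post change (not an intervention effect)*, and state which participants it uses.
2. For every outcome with follow-up data, whatever the omnibus F shows, report the between-arm difference in change from baseline to week 4 and to week 8 from the mixed model. Enter time as a factor, so that each week has its own contrast; the 1, 2, 3 coding given in Studies 2 and 3 would otherwise allow a single linear slope. Give the difference in scale points and standardised by a stated SD, each with a 95% CI.

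The pooled baseline SD is one reasonable denominator; the plan names none. Add a note that it comes from a range-restricted sample. Under the assumptions above it is about 0.73 to 0.87 of the unselected SD, so the standardised figure is larger than it would be in an unselected population.

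The cost is a change of wording and a few extra lines of output. No new data are needed.
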